# 5 Trial endpoints

#### 5.1 Primary endpoint

Infarct volume on day 5 on MRI among those who are alive.

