#### 5.2 Secondary endpoints

- Feasibility; defined as more than 75% of the nVNS treated patients completing treatment for five days or until discharge
- Tolerability; defined as less than 10% of the patients treated with nVNS having to abort treatment due to side effects
- Proportion of patients in whom <50% of the penumbra turned into ischemic core on noncontrast CT on day 3
- Clinical outcome (modified Rankin Scale, mRS) on day 90
- Occurrence of seizures or headache in the first 90 days
- Symptoms of depression, quality of life and cognitive status on day 90
- Overall survival in the first 90 days added after protocol publication

Two of the secondary endpoints mentioned in the publication of the study protocol are removed:

- Degree of blood-brain barrier leakage on day three measured with CT perfusion removed due to the inability to reliably quantify this parameter.
- NIHSS on day 5 or on day of discharge if earlier removed because it was considered not to have added value in addition to the radiological outcome and the 90-day clinical outcome.

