#### 5.3 Assessment of endpoints

Infarct volumes on MRI will be calculated by manually tracing hyperintense areas on the Diffusion-Weighted Imaging (DWI) sequence using MeVisLab version 3.4.4. Assessments will be done independently by two trained neuro-radiologists blinded to all patient information except for the side of the ischemic stroke. The average infarct volume of the two ratings will be used as the final infarct volume. A Bland-Altman plot will be made to describe interrater agreement. In case of substantial discrepancies between the two assessments the two raters will review their ratings and will trace the final infarct volume together in a consensus meeting.

Perfusion deficits (penumbra and core volumes) will be quantified using automated software (RAPID, iSchemaView).

The 90-day modified Rankin Scale (mRS) will be assessed with a telephone interview by a trained research nurse blinded to treatment allocation.

Symptoms of depression on day 90 will be assessed using the hospital anxiety and depression scale (HADS) questionnaire, quality of life with the EQ-5D and EQ VAS questionnaires, and cognitive status using the Telephone Interview for Cognitive Status (TICS) questionnaire. All questionnaires will be conducted by trained research personnel not blinded to treatment allocation.

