#### 6.2 Primary endpoint analysis

Linear regression analysis will be performed to assess the mean difference (MD) in the final infarct volumes between the two groups with corresponding 95% confidence intervals (CIs). The analysis is based on the intention-to-treat principle. Given the randomized design of the study no adjustments for potential outcome variation will be done with multivariable regression analysis. This decision was made after protocol publication. Instead, a sensitivity analysis will be performed with age, NIHSS at randomization and baseline infarct core on CTP as pre-specified covariates.

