## 7 Missing data and death

For all variables the proportion of missing values will be reported. For the primary endpoint, missing infarct volumes among those patients who are alive on day 5 will be imputed using a model containing the following information: NIHSS at randomization, baseline infarct core volume on CTP, infarct volume on NCCT on day 3 (if available), infarct volume on NCCT on day 5 (if available instead of MRI), treatment with IVT and/or EVT, TICI score post EVT, discharge before day 5, and death after day 5. We will use multiple imputation to generate 10 imputed datasets.

In case of missing questionnaires, these patients will be excluded from analyses on secondary endpoints regarding 90 day follow up. Furthermore, a subanalysis using the lowest and the highest values on the various scales will be conducted.

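### Does listing a day-5 NCCT volume, which exists only where the MRI does not, undermine the imputation of the primary endpoint?

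*SAP*

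**What the plan says.** The primary endpoint (SAP section 5.1) is "Infarct volume on day 5 on MRI among those who are alive", obtained by "manually tracing hyperintense areas on the Diffusion-Weighted Imaging (DWI) sequence" (section 5.3). Section 6.2 analyses it without adjustment: "Linear regression analysis will be performed to assess the mean difference (MD) in the final infarct volumes between the two groups".

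Section 7 deals with patients alive on day 5 who have no infarct volume. It lists the information on which the imputation will draw. Two items are NCCT volumes: "infarct volume on NCCT on day 3 (if available") and, separately, "infarct volume on NCCT on day 5 (if available instead of MRI"). The others are the NIHSS at randomization, baseline core on CTP, reperfusion treatment and its result, early discharge and later death. On the procedure it says only "We will use multiple imputation to generate 10 imputed datasets". It does not say whether the day-5 NCCT volume is a covariate of its own, is combined with the day-3 volume, or serves as a calibrated stand-in for the MRI volume.

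**The concern.** A predictor helps an imputation model only if its relation to the target can be learned from patients who have both. Here the condition attached to the day-5 NCCT volume rules that out: a patient who has it has no day-5 MRI. As a separate term its slope would come from a prior or from the starting values of the algorithm, not from data. Two analysts could then impute different values from the same database, and the same-day scan, probably the best substitute for the missing MRI, would be largely wasted.

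The primary endpoint is at stake. If patients scanned by CT tend to have larger infarcts, and one arm lacks MRI more often, poor imputed values could shift the estimated mean difference.

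**Working it through.** **Identifiability.** The SAP has no figure to reproduce here, so the first step is a count. Patients with day-5 MRI and day-5 NCCT both observed: 0 by the wording of section 7. The observed-data likelihood is therefore flat in the partial correlation between the two volumes, and a separate term has no estimable slope. Day-3 NCCT is different. It is not tied to missing MRI, and it is the scan for a secondary endpoint (section 5.2: "penumbra turned into ischemic core on noncontrast CT on day 3"), so its slope can be estimated.

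**How far imputed values can move the result.** From the SAP: 150 patients, 1:1, so 75 per arm. With complete data the standard error is SD x sqrt(2/75) = 0.163 SD. Assume 20% lack MRI: 0.20 x 150 = 30 patients, 15 per arm. An average imputation error of d SD in one arm, relative to the other, shifts the mean difference by 0.20 x d. A shift of 0.165 SD, about one standard error, needs d = 0.165 / 0.20 = 0.825 SD. Errors common to both arms cancel.

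**Simulation 1: unidentified correlation fixed at chosen values.** Assumed: SD 40 mL, true difference -10 mL, MRI missing at random, day-5 NCCT in 60% of those patients, day-3 NCCT in all, treatment arm in the imputation model, 10 imputations, 600 trials per setting.

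| MRI missing | Mean difference (mL) at partial correlation -0.9 / 0 / 0.5 / 0.9 | Standard error (mL) | Median change within a dataset, 0 to 0.9 (mL) | 90th percentile (mL) |
|---|---|---|---|---|
| 10% | -9.59 / -9.61 / -9.56 / -9.59 | 6.63 | 0.39 | 0.90 |
| 20% | -10.11 / -10.16 / -10.11 / -10.12 | 6.85 | 0.56 | 1.40 |
| 30% | -9.83 / -9.74 / -9.79 / -9.80 | 7.08 | 0.73 | 1.93 |

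The mean estimate moves by at most 9.83 - 9.74 = 0.09 mL. The median change within a dataset is 0.39/6.63 = 0.06 to 0.73/7.08 = 0.10 standard errors; at the 90th percentile it is 0.90/6.63 = 0.14 to 1.93/7.08 = 0.27. Part of that is random noise, because each imputation used fresh draws. Without arm in the model, going from 0 to 0.9 moves the mean by at most 8.96 - 8.56 = 0.40 mL, or 0.40/6.95 = 0.06 standard errors.

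**Simulation 2: MRI missing more often with larger infarcts.** Assumed: 20% without MRI, all with day-5 NCCT; correlation with MRI volume 0.6 (baseline), 0.85 (day-3 NCCT) and 0.95 (day-5 NCCT); log-odds of missing MRI rising 0.5 to 1.0 per SD of volume; day-3 NCCT in 50% to 100%; true effect 0.3 SD; standard error 0.165 to 0.171 SD with a separate term. Monte Carlo error of each bias is 0.002 to 0.004 SD. The last column subtracts the ends of the ranges, which presumes that they correspond.

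| Setting | Separate term, bias (SD) | One pooled NCCT term, bias (SD) | Difference (SD) |
|---|---|---|---|
| Missingness alike by arm | 0.001-0.017 | 0.001-0.005 | up to 0.012 |
| Control-arm odds 2.7 times higher | 0.019-0.062 | 0.014-0.038 | 0.005-0.024 |
| Alike, arm not in the model | 0.023-0.050 | 0.020-0.028 | 0.003-0.022 |
| Differing, arm not in the model | 0.037-0.089 | 0.032-0.055 | 0.005-0.034 |

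In standard errors, the part due to this item is at most 0.024/0.165 = 0.15 with arm in the model and 0.034/0.165 = 0.21 without. Total bias reaches 0.062/0.165 = 0.38 with arm and 0.089/0.165 = 0.54 without, but most of it remains after pooling. With skewed volumes and missingness differing by arm, the biases are 0.033 and 0.021 SD: a difference of 0.012, or 0.012/0.14 = 0.09 standard errors.

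**Is the alternative better?** Take control-arm odds 2.7 times higher, day-3 NCCT in 80% and log-odds 0.5. The separate term has bias -0.024 SD. The pooled term has -0.017 if day-5 NCCT is calibrated, -0.052 if it reads 0.3 SD low, +0.017 if 0.3 SD high, -0.029 if scaled by 0.8 and -0.006 if scaled by 1.2. Reading low multiplies the bias by 0.052/0.024 = 2.2.

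**The case for a change.** The best case for a change is this. Section 2 says the SAP was written partly to detail the handling of missing data, so the role of this item cannot be left to the protocol. The most literal reading, a covariate of its own, is the one that fails. The failure can be shown: with the same data, starting values random, strongly positive and strongly negative in their relation to MRI gave mean slopes of -0.13, 0.48 and -0.54, and errors of single imputed values of 0.59, 0.41 and 0.82 SD. Some simulated chains stopped on a singular matrix. Section 8 also allows a preliminary analysis at soft-lock by the people who will run the final one, so an open choice might be settled after results are seen. A sentence in section 7 would close it.

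The identifiability argument stands, and a sentence on the role of the scan would have made section 7 clearer. The rest carries less weight. Section 7 does not require a separate covariate; one common NCCT variable or a calibrated proxy fits its wording equally well. A singular matrix is a visible failure that would prompt an analyst to choose a workable form. The starting values correlated +0.95 and -0.95 with MRI are deliberately extreme, rest on 40 trials, and were reported for slopes and single values, not for the treatment difference. The freedom left at soft-lock is real, but the treatment difference responds to it only weakly. Finally, no wording can make the data supply the missing relation: pooling borrows the day-3 slope, which is itself an untestable assumption, and sets aside day-3 scans in patients who also have day-5 NCCT.

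**Conclusion.** No change to the plan is needed. Section 7 leaves open how one item enters the imputation model, and the one reading that cannot be estimated is not imposed. If that reading were followed, day-3 NCCT and the baseline data would still carry the imputation. The part of the bias due to this item is about 0.15 of a standard error at most with treatment arm in the model and about 0.2 without, against sampling error several times larger. Choosing another form is a trade-off: pooling helps somewhat if day-5 NCCT is calibrated and harms if it reads low. Extra sensitivity runs or counts of scans by arm would be added reporting, not a correction.

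These sizes depend on assumptions the SAP does not supply, chiefly up to 30% missing MRI, the correlations above, and control-arm odds of missing MRI no more than 2.7 times higher. The conclusion would weaken if MRI were missing much more often, or far more unevenly between arms. If some patients do have both day-5 scans, the identifiability problem eases, because the slope can be estimated from them. Whether treatment arm belongs in the imputation model is a separate matter and is not judged here.

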#### 3.2 Randomization

150 patients are randomized on a 1:1 basis to nVNS on top of best medical practice or best medical practice alone (including intravenous thrombolysis (IVT) and/or endovascular treatment (EVT)). Randomization is performed with Castor (castoredc.com) and is without stratification.

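### Ten imputed datasets with no fixed seed leave largely avoidable Monte Carlo noise in the primary result, which matters only if that result is borderline

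*SAP*

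**What the plan says.** The primary endpoint (SAP section 5.1) is "Infarct volume on day 5 on MRI among those who are alive". Section 6.2 gives the analysis: "Linear regression analysis will be performed to assess the mean difference (MD) in the final infarct volumes between the two groups", reported with a 95% confidence interval and unadjusted in the main analysis. Section 3.2 sets the trial size: "150 patients are randomized on a 1:1 basis to nVNS on top of best medical practice".

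Under section 7, infarct volumes missing in patients alive on day 5 are multiply imputed. The predictors include baseline severity, baseline core volume, reperfusion treatment, early discharge, and non-contrast CT infarct volumes on day 3 and day 5 where these exist. The number of datasets is set in one sentence: "We will use multiple imputation to generate 10 imputed datasets".

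The SAP gives no reason for ten, no random seed, no Monte Carlo error target and no expected missing rate. On the last it says only: "For all variables the proportion of missing values will be reported". It also states no significance level or p-value rule for the primary analysis.

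**The concern.** Multiple imputation draws random values. Two runs on the same data with different seeds therefore give slightly different mean differences, intervals and p-values. The fewer the datasets, the larger the difference. With ten datasets and no fixed seed, an interval that just excludes zero in one run may include it in the next.

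Two features make this worth a line in the plan.

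- Section 7 foresees survivors without a day-5 MRI, since early discharge and a CT done instead of MRI are both in the imputation model.
- Section 8 allows a preliminary analysis after a soft lock and a final one after the hard lock. Without a fixed seed and a small Monte Carlo error, a change between the two could come from data cleaning or from the imputation draws, and a reader could not tell which.

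An unspecified seed is also a free choice left to the analysts.

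**Working it through.** **Inputs from the SAP.** M = 10 imputations (section 7); N = 150 allocated 1:1, so at most 75 per arm (section 3.2); mean difference with 95% CI (section 6.2).

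**Assumed inputs.** FMI of 0.05 to 0.40, because the SAP gives no missing rate. The border is a 95% CI that just touches zero, which equals a two-sided p of 0.05. The SAP derives the ten from nothing, so there is no stated figure to reproduce.

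**Step 1: precision.** Relative efficiency against unlimited imputations is 1/(1 + FMI/M). The Monte Carlo SD of the pooled estimate, in standard errors, is sqrt(FMI/M).

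| FMI | Relative efficiency, M = 10 | Monte Carlo SD, M = 10 | Monte Carlo SD, M = 100 |
|---|---|---|---|
| 0.05 | 0.995 | 0.071 | 0.022 |
| 0.10 | 0.990 | 0.100 | 0.032 |
| 0.20 | 0.980 | 0.141 | 0.045 |
| 0.30 | 0.971 | 0.173 | 0.055 |
| 0.40 | 0.962 | 0.200 | 0.063 |

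The efficiency loss with ten datasets is therefore 0.5% to about 4%.

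**Step 2: hand check of a borderline result.** Suppose unlimited imputation would give p = 0.04, so z = 2.054. At FMI 0.10 and M = 10, 95% of runs lie within 2.054 ± 1.96 × 0.100, that is z from 1.858 to 2.250, or p from 0.063 to 0.024. The chance that z falls below 1.96 is Φ((1.96 − 2.054)/0.100) = Φ(−0.94), about 17%.

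**Step 3: fuller calculation.** The hand check ignores noise in the estimated between-imputation variance B. Here the pooled estimate is drawn with variance B/M and the variance estimate as B × χ²(M − 1)/(M − 1). Rubin's rules with Barnard-Rubin degrees of freedom are then applied (N = 150; 200,000 draws per cell). For an unlimited-imputation p of 0.04:

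| FMI | 95% range of p, M = 10 | CI includes zero, M = 10 | M = 50 | M = 100 |
|---|---|---|---|---|
| 0.05 | 0.028–0.057 | 11.7% | 0.2% | 0.0% |
| 0.10 | 0.024–0.068 | 23.0% | 3.0% | 0.3% |
| 0.20 | 0.018–0.090 | 34.9% | 11.6% | 4.2% |
| 0.30 | 0.014–0.114 | 41.5% | 19.3% | 9.6% |

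The figures exceed the hand check (23.0% against 17% at FMI 0.10) partly because Rubin's rules with few datasets widen the interval slightly, through the added B/M and fewer degrees of freedom. In the other direction, for p = 0.06, the CI excludes zero in 12.5%, 20.5%, 27.2% and 29.7% of runs with M = 10.

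**Step 4: away from the border, M = 10.** For p = 0.02 the CI includes zero in 0.0%, 0.1%, 3.3% and 9.7% of runs at the same four FMI values. For p = 0.01 it does so in 1.4% or less.

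**Step 5: what missing rate would give these FMI values?** Complete imputation was simulated with 75 per arm, normal outcomes, data missing completely at random, arm in the imputation model, and one predictor with an assumed R² of 0.3 or 0.6. Only datasets with a reference p (M = 400) of 0.03 to 0.05 were kept.

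| Missing scans | FMI | SD of p, M = 10 | Runs with p above 0.05, M = 10 |
|---|---|---|---|
| 5% | 0.02–0.04 | 0.005–0.006 | 11–13% |
| 10% | 0.04–0.08 | 0.007–0.009 | 16–19% |
| 20% | 0.10–0.15 | 0.011–0.015 | 22–33% |
| 30% | 0.15–0.24 | 0.016–0.021 | 31–34% |

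**The case against.** The strongest reply is that nothing here is wrong. The SAP names the method, lists the predictors and fixes the number of datasets before database lock. Ten imputations give valid inference at negligible loss of precision. That stands, and it is why the point is minor.

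The size is also uncertain, and probably at the lower end. Deaths before day 5 fall outside the endpoint, so only missing scans in survivors are imputed, and the CT volumes may be close proxies for the MRI volume. In step 5 an FMI of 0.20 needed close to 30% missing scans, and no scenario reached 0.30. With 5% missing, the SD of p was only about 0.005. This stands too. Even then, 11–13% of runs with a reference p of 0.03 to 0.05 changed side.

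Three stronger readings are tempting, and the SAP does not support them.

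- A reader might infer that the primary conclusion will depend on the seed. It can do so only if the result is borderline, and step 4 shows how fast the effect fades.
- A reader might infer that a planned 0.05 test is at risk. The SAP states only a 95% CI, so the threshold is an inference. The equivalent statement is whether the interval includes zero.
- A reader might infer that more imputations would remove the noise. They would not: with 100 datasets and FMI 0.30, 9.6% of runs at p = 0.04 still cross.

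**Conclusion.** The point holds as a free improvement in reproducibility, not as an error. Ten datasets introduce no bias, but leave the primary mean difference with seed-dependent noise of 7% to 17% of a standard error for FMI 0.05 to 0.30, and the plan fixes neither a seed nor an error check. For a result near p = 0.04, that noise puts the interval on the other side of zero in roughly one run in nine (FMI 0.05) to two in five (FMI 0.30). With 100 datasets the share is one in ten or fewer. For clear results it is of no consequence.

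The figures rest on an assumed FMI, on normal theory and, in step 5, on data missing completely at random with arm in the imputation model. They concern the number of imputations only and say nothing on whether the imputation model itself is adequate.

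**What to change.** In SAP section 7:

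- replace ten by at least 100 imputed datasets;
- state the random seed in advance, and use it for both the preliminary and the final analysis. This prevents a choice among seeds but does not reduce the noise;
- report the Monte Carlo error of the pooled mean difference, sqrt(B/M), next to its standard error, so that a reader can see whether a borderline interval is stable.

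The cost is one changed number and two added sentences. Computing time for 150 patients is trivial. The estimand, the analysis model and the sample size stay as they are.
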